Study Design and Protocol

Evaluation of a Milk-Based Nutritional Supplement to Effect a Positive Change in Bone Health in Post-Menopausal Women at Risk of Osteoporosis.

Background:

The process of bone remodeling exhibits pronounced diurnal pattern that is important for bone health. A balanced rate of bone resorption is required to maintain bone health, a balance that can be disturbed during the life-cycle to effect net rate of formation (as occurs during growth and development to adulthood) or net resorption (as occurs, for example, during the menopause). Bone turnover is a nutritionally modulated process. Research recently completed by this research group (2017_06_03_EHS) suggests that a milk-based protein supplement (MBPS) can modulate beneficially the rate of bone resorption over the time period when bone remodeling is most active i.e. late evening/overnight. In this novel approach to the timing of nutrient ingestion, the proposed nutrient intervention seeks to modify (reduce) the rate of bone resorption and promote the rate of bone formation to the benefit of bone health in this at risk population.

Study design:

A block randomised, controlled study among healthy, post-menopausal women with osteopenia receiving a milk-based protein supplement (MBPS) during late night or not (CONTROL) for a period of 24 weeks.

Procedures:

Subjects: Post-menopausal women aged 50 to 70 y

Subject screening: Osteopenia as determined by site-specific BMD (DXA), clinical history, blood screen, previous 3m of intake of calcium and Vit D by Food Frequency Questionnaire (FFQ) will be conducted to qualify inclusion/exclusion criteria

Inclusion Criteria: Post-menopausal women aged 50-70y assessed by site-specific BMD to be osteopenic (BMD T-score between -1.0 to -2.5), assessed by clinical screen to be otherwise healthy and free from other illness, women with normal blood sugar (assessed by fasting blood sugar 3.9 to 5.8 mmol/L), thyroid function (serum TSH 0.50 - 4.4 mU/L), vitamin D (above 50 nmol/L), kidney function (serum creatinine 50 - 98 umol/L), not on medications likely to influence the study outcome (steroid or anti-convulsion drugs)

Exclusion criteria: Women with osteoporosis (BMD T-score less than -2.5) or/and any other illness. Women with blood sugar, TSH levels, vitamin D and/or creatinine measurements outside of the values mentioned above and/or on medications.

Experimental protocol: subjects qualifying and willing to participate will undertake the following tasks;

Week 1: Test Day 1

1. Arrive between 08:00 to 09:00h after an overnight fast from 22:00h the previous evening;
2. Empty bladder and collect and retain urine for a period of 24h.
3. Provide a blood sample from a superficial arm vein; total blood draw is 5ml
4. Subjects will be instructed as to the completion of a 7-day weighed food intake record and asked to complete a trial 24h record prior to returning the following day.

Week 1: Test Day 2

1. Return the following day and provide a first-pass urine sample, provide a blood sample from a superficial arm vein; total blood draw is 5ml
2. The dietitian will then review the entries on the 24h dietary record sheet with the subject and resolve any potential conflicts. The subject will then be asked to complete the full 7 day weighed food intake record.

Nutritional Supplement and Bone Health in Post-Menopausal Women (MBPS)

Ethical approval number: 2018_04_05_EHS

Date of Approval 13th Aug 2018

Week 2: Test Day 3

1. Once the food intake record is completed, the dietitian will review the entries and resolve any potential conflicts with the participant.

2. MBPS group: The subject will be asked to take the supplement the MBPS as prescribed i.e. prior to retirement each night.

Control group: The subject will be free living. No change in dietary behaviour will be required.

Composition of MBPM - 25g of milk-based proteins + 1000mg dairy-based calcium fortified with 40ug Vit D flavoured and textured. All formulations to be supplied food grade and product tested by Dairygold Co-operative Society, Mitchelstown, Ireland.

Week 12: Test Day 4

1. Subjects will return for a DXA scan between 07:30 and 09:30h after an overnight fast from 22:00h the previous evening.

Week 24: Test Day 5

1. Subjects will return and follow the same protocol as on Test Day 1 and Test Day 2.

2. Subjects will also receive a DXA scan on the first return visit.

Throughout the study period:

The MBPS group will be contacted at regular intervals to check compliance and will return to PESS to collect additional supplements.

Analytical methods:

The International Osteoporosis Foundation I.O.F. recommended the biomarker CTX for bone resorption and P1NP for bone formation in serum and pyridinoline (PYD), deoxypyridinoline (DPD) and NTX excretion normalised for urinary creatinine as the respective biomarkers in urine.

- i. In total, 240 (60 subjects * 2 samples * 2 d) morning blood samples will be collected. Separated aliquots will be frozen @ -80C and batch analysed for CTX (biomarker of resorption), P1NP (biomarker of formation).
- ii. In total, 240 (60 subjects * 2 samples * 2 d) 24h urine samples will be collected. Aliquots will be frozen @ -80C and batch analysed for uPYD, uDPD, and uNTX (biomarkers of resorption) normalised to urinary creatinine.

UNIVERSITY of LIMERICK

OLLS COIL LUIMNIGH

Statistical Plan

Evaluation of a Milk-Based Nutritional Supplement to Effect a Positive Change in Bone Health in Post-Menopausal Women at Risk of Osteoporosis.

Research Question or hypothesis:

Ho: Compared to habitual dietary intake, ingestion of a milk protein-based supplement in the evening each day for a period of 24 weeks will not affect site specific bone mineral density of post-menopausal women with osteopenia

Ho: Compared to habitual dietary intake, ingestion of a milk protein-based supplement in the evening each day for a period of 24 weeks will not affect fasting serum and diurnal (24h) rates of bone turnover in post-menopausal women with osteopenia.

Brief Background: In a novel approach to the timing of nutrient ingestion, the proposed nutrient intervention seeks to modify (reduce) the rate of bone resorption and promote the rate of bone formation to the benefit of bone health in post-menopausal women aged 50 to 70y diagnosed with osteopenia.

Study Design: A block randomised design with a TREATMENT group maintaining habitual dietary intake with evening MBPS and a CONTROL group maintaining habitual dietary intake only.

Participants: 60 post-menopausal women aged 50 to 70y diagnosed with osteopenia.

Previous studies conducted by the research team (Norton et al. 2016 Journal of Nutrition, 146(1), 65–69) required a sample of 30 per group to give statistical power of >80 % at alpha 0.05 with delta change in BMD of 0.017 gcm² compared to a control group for period of 6 months.

Statistical Analysis: ANOVA(R)

Independent variables:

Group [2]

TREATMENT (MBPM) and CONTROL

TIME [2]

Pre and Post 24 week intervention

Dependent variables:

Bone Mineral Density (BMD)

Serum CTX (bone resorption)

Serum N1PD (bone formation)

Urine DPD/Creatinine (bone resorption)

Urine NTX/Creatinine (bone resorption)

Significance of effect on bone remodeling will be analysed by 2 Factor ANOVA(R)

Notes:

- i. Violation to normality (Shapiro – Wilk) data will be transformed by rank for analysis
- ii. Violation to homogeneity of variance-covariance matrices (Mauchly's W), correction factors (Green-House Geisser, Huynh-Feld) will be applied
- iii. Violation to homogeneity of variance for post-hoc analysis (Levene's or Brown-Forsythe Test), Welch-Satterthwaite corrections will be applied.
- iv. Bonferroni corrected post-hoc comparisons

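### The SAP's >80% power for BMD refers to 60 complete pre/post pairs: no allowance is made for losses, and the scheduled Week 12 DXA is left out of the analysis

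*SAP*

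**What the plan says.** The SAP, under Participants, plans "60 post-menopausal women aged 50 to 70y diagnosed with osteopenia". It justifies this by earlier work of the team, which "required a sample of 30 per group to give statistical power of >80 % at alpha 0.05", for a difference in BMD change of 0.017 against control over six months. No SD, sidedness or dropout rate is given.

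Under Statistical Analysis the method is a two-factor repeated-measures ANOVA with group at two levels and TIME at two levels, "Pre and Post 24 week intervention". The four notes cover normality, sphericity, unequal variances and Bonferroni correction. None covers missing data or says which women are analysed.

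The protocol schedules DXA at screening, at Week 12 ("Subjects will return for a DXA scan between 07:30 and 09:30h after an overnight fast from 22:00h the previous evening") and at Week 24 ("Subjects will also receive a DXA scan on the first return visit"). The Week 12 visit is not restricted to one group. Under Analytical methods the sample budget is "In total, 240 (60 subjects * 2 samples * 2 d) morning blood samples will be collected", which counts every woman at both baseline and Week 24.

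**The concern.** The planned number equals the number called required, so the plan has no stated margin. With two time levels, the group-by-time test is a two-sample comparison of change scores, and a missing Week 24 scan removes the woman altogether. A null BMD result would be read against >80% power, although that figure describes a trial that loses nobody over 24 weeks.

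The second issue is the unused scan. A woman who leaves after Week 12 has already given a second BMD measurement, which the analysis discards. If leaving is related to BMD change by Week 12, the women with complete pairs are a selected group, and the estimated difference can be biased.

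**Working it through.** **Inputs.** From the SAP: 60 participants, 30 per group, power >80%, alpha 0.05, difference 0.017, TIME at two levels. From the protocol: DXA at screening, Week 12 and Week 24. Assumed: 1:1 allocation (from 60 = 2 × 30), a two-sided test unless stated, and losses of 10% or 20%.

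**Step 1: the plan's own figure.** 60 / 2 = 30, equal to the stated requirement, so the margin is 0. The power claim cannot be reproduced without the SD of change, but it can be bounded. For n per group and d = 0.017 / SD, power comes from the noncentral t with 2n − 2 degrees of freedom and noncentrality d / √(2/n).

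- 80% at n = 30 needs d = 0.7356, that is SD = 0.017 / 0.7356 = 0.0231.
- 80% at n = 29 needs d = 0.7487, that is SD = 0.017 / 0.7487 = 0.0227.

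If 30 is the smallest n that exceeds 80%, d lies between these two values.

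**Step 2: power after losses, on that reading.**

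| Evaluable per group | Power, two-sided |
|---|---|
| 30 and 30 | 80.0–81.4% |
| 30 and 29 (one loss) | 79.3–80.7% |
| 29 and 29 | 78.6–80.0% |
| 27 and 27 (10% loss) | 75.6–77.0% |
| 24 and 24 (20% loss) | 70.4–71.9% |

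For one loss the noncentrality is d / √(1/30 + 1/29) with 57 degrees of freedom. A one-sided test gives 76.1–77.4% at 27 and 71.6–72.9% at 24.

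**Step 3: the other reading.** The SAP says more than 80%, so 30 may contain slack. To keep 80% at 27 per group, power at 30 must be at least 84.1%; at 24 per group, 88.2%. If power at 30 were 90%, it would still be 86.6% at 27 and 82.3% at 24.

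**Step 4: what the Week 12 scan recovers under random loss.** Suppose 6 of 30 women per group leave after Week 12, and let ρ be the correlation between the Week 12 and Week 24 changes. The effective number per group is 24 / (1 − 0.2ρ²):

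- ρ = 0.5: 24 / 0.95 = 25.3
- ρ = 0.7: 24 / 0.902 = 26.6

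The gain is 1.3 to 2.6 women per group. In simulation (SD 0.0231, effect at Week 12 half that at Week 24), power was about 70% with complete pairs and 72–74% with the Week 12 scan.

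**Step 5: selective loss, as an illustration only.** In the same setting, control women who had lost more bone by Week 12 were made more likely to leave. The complete-pair difference shrank from 0.017 to 0.0143 (ρ = 0.5) or 0.0131 (ρ = 0.7), with power 56% or 51%. With the Week 12 scan in the model the difference stayed at 0.017, with power 72–74%. With no true effect and ρ = 0.6, the false-positive rate was 8.0% with complete pairs and 4.8% with the Week 12 scan.

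**The case against.** A reader might infer that any dropout takes the trial below 80% power. The documents do not support that. The 30 comes from earlier work; its SD is not given, and it may already hold a margin. Even on the tightest reading, one loss gives 79.3–80.7%, which straddles 80%. What follows for any SD is only that the evaluable number falls below the 30 called required.

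A reader might also infer that the trial must enrol 68 women (30 / 0.9 = 33.3, so 34 per group) or 76 (30 / 0.8 = 37.5, so 38 per group). With no stated dropout rate and no demonstrated shortfall, the documents do not establish that need, and 8 or 16 extra women are not cheap. Nor is 240 wrong as a count: 60 × 2 × 2 = 240, and it can stand as a maximum.

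Three parts of the reading are inferred. The 60 could be meant as evaluable women, although the SAP says participants and the protocol says subjects. The 1:1 split is not written. Exclusion of women without a Week 24 scan follows from a two-level repeated-measures ANOVA with no imputation rule, but is not put in words. One sentence in the SAP would settle each.

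On the model, a pre/post group-by-time test is a legitimate test of the 24-week hypothesis, and under random loss the gain from the Week 12 scan is small. The selective-loss figures rest on an assumed mechanism in which leaving depends only on the observed Week 12 change plus noise. Data are then missing at random by construction, and recovery of 0.017 is expected. They show what could happen, not what this trial should expect. It remains true that the planned analysis discards data already scheduled.

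**Conclusion.** The point holds as a gap in planning and analysis, not as an arithmetic error. The >80% applies to 30 complete pre/post pairs per group; the plan says nothing about losses and leaves the Week 12 DXA unused. If all 60 women complete, no shortfall is shown.

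If 30 is the smallest number exceeding 80%, two-sided, losses of 10% and 20% bring power to about 76–77% and 70–72%. If planned power was at least 84% or 88%, those losses are absorbed. The documents do not say which case applies, and both loss rates are assumptions. The clearest improvement is to use the Week 12 scan, mainly as protection should leaving be related to BMD change by Week 12.

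**What to change.** **1. SAP, analysis of BMD.** Replace the pre/post ANOVA for BMD with text such as:

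> BMD at baseline, Week 12 and Week 24 will be analysed in a mixed model for repeated measures with group, time and group-by-time terms and an unstructured covariance. All randomised women with a baseline scan will be included in the group assigned. The test is the group difference in change from baseline at Week 24.

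The SAP should also say which scan is the baseline: the protocol names DXA at screening but not on Test Days 1 or 2.

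*Cost.* No new visits or scans, and a little more analysis work. The model assumes data missing at random, adds nothing for women lost before Week 12, and under random loss recovers only about 1 to 3 women per group. The SAP's notes on rank transformation and sphericity correction would need adapting for this outcome.

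**2. SAP, Participants.** Keep enrolment at 60, state that >80% power refers to 30 evaluable women per group, and give the SD of change, the sidedness, the expected loss and the power at the resulting evaluable number.

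*Cost.* A few sentences, using inputs that the original calculation must have had. The quoted power may turn out lower than >80%.

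Larger enrolment is not asked for. If the sponsor chooses it, sample counts of 68 × 2 × 2 = 272 or 76 × 2 × 2 = 304 should be labelled as maxima. With the assumed losses before Week 24, about 68 × 2 + 61.2 × 2 = 258 or 76 × 2 + 60.8 × 2 = 274 would be expected.

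### The BMD test uses only the screening and Week 24 scans, so a woman without a Week 24 scan drops out of it and the scheduled Week 12 DXA is unused

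*SAP*

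**What the plan says.** The SAP (Statistical Analysis) specifies a two-factor repeated-measures ANOVA with Group [2] and TIME [2]. The time levels are "Pre and Post 24 week intervention", and BMD is the first dependent variable listed. Under note ii, if the covariance assumption fails, "correction factors (Green-House Geisser, Huynh-Feld) will be applied".

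The protocol schedules three DXA scans:

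- **Screening:** "Osteopenia as determined by site-specific BMD (DXA), clinical history, blood screen" (Subject screening).
- **Week 12, Test Day 4:** "Subjects will return for a DXA scan between 07:30 and 09:30h". The scan is the only procedure that day.
- **Week 24, Test Day 5:** a scan at the first return visit.

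For sample size, the SAP (Participants) plans "60 post-menopausal women aged 50 to 70y diagnosed with osteopenia". It says that the team's earlier work "required a sample of 30 per group to give statistical power of" more than 80% at alpha 0.05, "with delta change in BMD of 0.017" g/cm² against control over 6 months.

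Neither document states an SD, an expected loss rate, an analysis population or a rule for missing scans.

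**The concern.** BMD is the subject of the first hypothesis and the basis of the sample size, so this is the trial's central test. Three things follow from giving it two time levels.

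- **Women lost.** A woman scanned at screening and Week 12 but not at Week 24 adds nothing to the test.
- **Assumption.** The comparison rests on women with a Week 24 scan being like those without one. One arm takes a nightly product for 24 weeks and the other changes nothing, so loss could differ between arms.
- **Unclear role of Week 12.** The scan is collected from all women, but the SAP does not say how it is used. The sphericity corrections in note ii can act only with three or more time levels. That does not prove Week 12 was meant to be included, but it leaves the number of BMD visits in the model unclear.

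**Working it through.** **1. What the two-level test does.** With times Pre and Post, the group-by-time F test is the two-sample t test on D = Post − Pre. Without a Post value D does not exist, so her record drops out unless a missing-data rule says otherwise, and none is given. The lower bound of the sphericity epsilon is 1/(k − 1). For k = 2 it is 1, so no correction is possible; for k = 3 it is 0.5.

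**2. Inputs.** From the SAP: alpha 0.05, delta 0.017 g/cm², 30 per group, power above 80%. Assumed: a two-sided test (the SAP does not state sidedness, but its null hypothesis is non-directional), the SD of change, the loss rates (10, 15 and 20%, equal in both arms) and the correlation r between 12-week and 24-week changes (0.5 to 0.8). The SAP names no BMD site, so the figures describe a single site.

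**3. The plan's own figure.** Power comes from the noncentral t distribution with 2n − 2 degrees of freedom and noncentrality delta / (SD × √(2/n)). Without an SD, 30 per group cannot be reproduced. Solving for the SD that gives exactly 80% power:

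| Analysed per arm | Loss from 30 | SD giving 80% power |
|---|---|---|
| 30 | 0% | 0.0231 |
| 29 | – | 0.0227 |
| 27 | 10% | 0.0219 |
| 25.5 | 15% | 0.0212 |
| 24 | 20% | 0.0206 |

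Power therefore falls below 80% at 10, 15 or 20% loss only if the SD exceeds 0.0219, 0.0212 or 0.0206. If 30 was the smallest n reaching 80%, the SD lies between 0.0227 (where 29 would just suffice) and 0.0231.

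**4. Power after loss.**

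| SD | No loss | 10% | 15% | 20% |
|---|---|---|---|---|
| 0.0231 | 80.0% | 75.6% | 73.1% | 70.4% |
| 0.0227 | 81.4% | 77.0% | 74.6% | 71.9% |
| 0.020 | 89.9% | 86.5% | 84.5% | 82.2% |

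The last row shows the slack that a smaller SD would leave.

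**5. What the Week 12 scan recovers.** Let n24 be the women per arm with a Week 24 scan, and n12 those with a Week 12 scan (everyone in n24 plus the lost women scanned at Week 12). A likelihood-based model gives

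variance of the mean 24-week change per arm = SD² × [(1 − r²)/n24 + r²/n12],

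so the effective n is 1 / [(1 − r²)/n24 + r²/n12].

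Example: 15% loss, half of the lost women scanned at Week 12, so n24 = 25.5 and n12 = 25.5 + 2.25 = 27.75.

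- r = 0.5: 0.75/25.5 + 0.25/27.75 = 0.03842, effective n 26.0, power about 74%.
- r = 0.8: 0.36/25.5 + 0.64/27.75 = 0.03718, effective n 26.9, power about 75%.

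All cases at SD 0.0231:

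| Loss | Two-level ANOVA | Half of lost scanned at Week 12 | All of lost scanned at Week 12 |
|---|---|---|---|
| 10% | 75.6% | 76-77% | 77-78% |
| 15% | 73.1% | 74-75% | 75-77% |
| 20% | 70.4% | 72-74% | 73-76% |

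In points, the gains are about 0.5-1.4, 1-2 and 1-3 if half were scanned, and 1-3, 2-4 and 2-6 if all were. At SD 0.0227 they are almost the same.

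**The case against.** - **Exclusion is inferred.** The SAP nowhere says that women without a Week 24 scan are excluded. True; it follows from the method together with the absence of any other rule. An unstated rule would be no better.
- **Sixty may be a completer target.** The protocol's sample counts (60 subjects, 2 samples, 2 days, 240 in total) would fit that reading. The documents do not settle it. It bears on the power remark, not on the unused scan or the dropped records.
- **No shortfall is shown.** This stands. The figures between 70% and 77% require 30 to have been the minimum n. A one-sided test would also move the SD thresholds to about 0.0248, 0.0241 and 0.0233.
- **Pre/Post 24 matches the hypothesis.** It does, and the proposed test keeps the 24-week question. Week 12 enters only as information about women whose Week 24 value is missing.
- **The gain is small and may be nil.** This stands too. The model does not replace an allowance for loss. Its case rests as much on the weaker missing-data assumption and on stating how Week 12 is used as on power.

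**Conclusion.** The concern holds. As written, the BMD test cannot use the Week 12 scan and loses every woman without a Week 24 scan, and nothing elsewhere in the documents repairs this. The structural part rests only on the two stated time levels, the three scheduled scans and the lack of a missing-data rule. The cost in power is conditional: roughly 3 to 10 points at 10-20% loss if 30 per arm was only just enough, with power still above 80% if the SD of change is 0.0206 or less. The three-visit model recovers part of that, under the assumed correlations and only if some of the lost women attended Week 12. This is an improvement the plan should make at little cost. It is not evidence that the trial is underpowered.

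**What to change.** Replace the BMD analysis in the SAP with a mixed model fitted to all randomised women, using the screening, Week 12 and Week 24 scans. Include group, visit as a categorical factor and their interaction, with an unstructured covariance. Name the Week 24 contrast, the difference between arms in change from screening to Week 24, as the test. Add a line saying that the note ii correction is not used for this model and how the rank transform in note i applies to it. When the sample-size paragraph is next edited, word the power above 80% as applying to 30 completers per arm.

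The cost is a little analysis work and an explicit missing-at-random assumption given the observed scans. No visit, scan or participant is added. If every woman attends all three scans, the estimated Week 24 contrast equals the difference in mean change that the two-level analysis would give. The turnover markers are sampled only at the start and at Week 24, so this change does not apply to them.

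### The group-by-time ANOVA names no deciding treatment test and does not adjust for baseline; ANCOVA would be more precise for the turnover markers, with little or no gain for BMD

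*SAP*

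**What the plan says.** The SAP's Statistical Analysis section sets out a repeated-measures ANOVA with two factors. The between-woman factor is "TREATMENT (MBPM) and CONTROL" and the within-woman factor is "Pre and Post 24 week intervention". The same model serves BMD, serum CTX, the serum formation marker and two creatinine-corrected urine markers. The operative sentence is "Significance of effect on bone remodeling will be analysed by 2 Factor ANOVA(R".

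Baseline enters only as the first level of TIME, and no covariate is listed. Of the three F-tests that the model produces (group, time, group by time), none is designated as the test of treatment, and no effect estimate or interval is specified. Note iv adds "Bonferroni corrected post-hoc comparisons" without listing the comparisons. The Protocol has no analysis section that settles the matter.

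The SAP's Participants section gives the only power statement, and it concerns BMD: "delta change in BMD of 0.017 gcm² compared to a control group for period of 6 months". That wording describes a between-arm difference in change, which is the group-by-time contrast.

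**The concern.** There are two linked points.

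**The deciding test is left open.** Both null hypotheses compare the supplement with habitual diet, so the test must compare arms after treatment. The group main effect averages the pre-treatment value with the Week 24 value and so halves the treatment difference. Within-arm pre/post comparisons, which Note iv leaves possible, do not compare the arms at all. A reader can infer group by time from the power statement, but the SAP does not specify it.

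**Baseline is used inefficiently.** With two groups and two times, group by time is exactly a t-test on change scores. It subtracts baseline with a slope of 1. When the pre-post correlation is below 1 and the pre and post SDs are equal, that over-corrects. The result is a wider interval than the data allow and, when the arms differ by chance at baseline, a conditional bias of size (1 − correlation) × baseline difference.

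The second null hypothesis depends on the turnover markers, for which no power is stated. Baseline markers are already collected (Protocol, Analytical methods, item i: "In total, 240 (60 subjects * 2 samples * 2 d) morning blood samples will be collected", read here as two days at baseline and two at Week 24), so the lost precision could be recovered from data in hand.

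**Working it through.** **The plan's own figure.** The SAP says its earlier work "required a sample of 30 per group to give statistical power of >80 % at alpha 0.05" for a BMD difference of 0.017. No SD is given, so this cannot be reproduced, only inverted. Two-sided, with the normal approximation: SD = 0.017 / [(1.960 + 0.842) × √(2/30)] = 0.0235 g/cm². This figure is used below as the SD of BMD change.

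**Inputs.** From the SAP: 60 women, 30 per arm, alpha 0.05 (two-sided assumed). Assumed, because the documents give none: pre-post correlation ρ, equal pre and post SDs, and a marker effect of 0.5 SD.

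**Variance.** Per woman, in units of the outcome variance:

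- change score: 2(1 − ρ)
- ANCOVA: (1 − ρ²) × (1 + 1/56), where the last factor is the cost of estimating the slope (N − 4 = 56)
- ratio of ANCOVA to change score: (1 + ρ)/2 × 57/56

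At ρ = 0.5 the ratio is 0.75 × 57/56 = 0.763. The saving is 60 × (1 − 0.763), or about 14 women.

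| ρ | Variance ratio | Saving, of 60 women | Power, group by time | Power, ANCOVA |
|---|---|---|---|---|
| 0.5 | 0.763 | 14 | 48% | 59% |
| 0.6 | 0.814 | 11 | 57% | 66% |
| 0.7 | 0.865 | 8 | 69% | 75% |
| 0.8 | 0.916 | 5 | 85% | 88% |
| 0.9 | 0.967 | 2 | – | – |

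Power is by noncentral t (58 df for change, 57 df for ANCOVA). Simulation gives matching variance ratios. The ratio reaches 1 at ρ = 0.965.

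**BMD.** If the SD of change is 0.0235, then ρ = 1 − 0.0235²/(2 × SD²). An assumed between-woman SD of 0.08 or 0.12 g/cm² gives ρ of about 0.96 or 0.98 and a ratio of 0.998 or 1.008, so there is no gain or a loss under 1%.

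**Averaging the two sampling days.** If the two samples at each time point are averaged, ρ becomes ρ / [(1 + w)/2], where w is the between-day correlation (assumed 0.80 to 0.95). Single-sample ρ of 0.5, 0.6, 0.7 and 0.8 becomes 0.51–0.56, 0.62–0.67, 0.72–0.78 and 0.82–0.89. The variance ratio becomes 0.77–0.79, 0.82–0.85, 0.87–0.90 and 0.93–0.96. The gain shrinks but remains.

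**Chance imbalance.** A baseline difference above 0.4 SD has z = 0.4/√(2/30) = 1.55, a probability of about 12%. Type I error of the group-by-time test, from 2,000,000 draws per ρ:

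| ρ | Imbalance above 0.4 SD | Otherwise | Overall |
|---|---|---|---|
| 0.5 | 13.5% | 3.9% | 5% |
| 0.6 | 11.8% | 4.1% | 5% |
| 0.7 | 10.0% | 4.3% | 5% |
| 0.8 | 8.4% | 4.6% | 5% |

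ANCOVA stays at about 5% in both sets (4.8% to 5.4% in 80,000 simulated trials).

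**Group main effect as the test.** The effect is halved and set against SD × √((1 + ρ)/2). For the 0.5 SD marker effect (0.25 SD after halving), power is 17% to 20% at ρ from 0.8 down to 0.5. For BMD (0.0085 g/cm² after halving, between-woman SD 0.08 to 0.12), it is 6% to 7%.

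**The case against.** The strongest reply is that a two-by-two repeated-measures ANOVA is a standard analysis with correct overall type I error, so the covariate point is one of preference. The planned test is indeed valid. The raised error applies only to the 12% of randomisations beyond a chosen cut-off and is offset in the rest. The covariate point therefore concerns precision and behaviour under imbalance.

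The size of the gain is also assumed. No document gives ρ, and the ratio formula needs equal pre and post SDs. If the Week 24 SD is 1.2 times the baseline SD, the ratios at ρ of 0.5, 0.6, 0.7 and 0.8 become 0.89, 0.94, 0.98 and 1.01. If it is 0.8 times, they are 0.58 to 0.65. This changes the size of the gain but not its direction at moderate ρ. Apart from the slope-estimation factor, ANCOVA never has the larger variance, so the worst loss is 57/56, about 2%.

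ANCOVA does little for BMD, the only outcome with a power statement. That stands, though the T-score entry band may narrow baseline BMD. A between-woman SD of 0.05 would give ρ of about 0.89, a ratio of 0.96, and main-effect power of about 10%.

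SAP Note i ranks the data if normality fails, and the figures above do not carry over directly to ranks. That also stands. The rank rule can be applied within ANCOVA, but the SAP has to say how.

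Finally, the power statement already points to group by time, so one sentence would settle the unnamed test without ANCOVA. That is correct, and the fix below allows for it.

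**Conclusion.** The concern holds. The SAP has no baseline covariate and names no deciding test of treatment.

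The unnamed test is the firmer half, because it rests on the text alone. One available reading, the group main effect, would leave 17% to 20% power for a 0.5 SD marker effect and 6% to 7% for the BMD difference in the power statement, under the SDs assumed.

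The covariate half is a matter of efficiency. With equal SDs and ρ of 0.5 to 0.8, ANCOVA removes about 24% down to 8% of the variance for the markers, and 3% at ρ of 0.9. For BMD the expected result lies between a gain of about 4% and a loss of about 1%. The values of ρ, the SDs and the marker effect are all assumptions. The planned analysis is not invalid, but the improvement is cheap and worth making.

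**What to change.** For each outcome, specify ANCOVA of the Week 24 value on group with the baseline value as covariate as the single test of treatment effect. Report the group coefficient with its 95% CI. State that treatment conclusions will not rest on the group or time main effects or on within-arm pre/post comparisons.

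Two details belong in the same text: whether the two days' samples at each time point are averaged, and how the ranking rule in Note i applies to the ANCOVA (a coefficient from ranked data is in rank units).

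If the ANOVA is kept, for BMD or throughout, name group by time as the only treatment test and give the between-arm difference in change with its 95% CI.

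The cost is SAP wording only, with no new visits, samples or participants. One degree of freedom goes to the covariate; for BMD the loss of precision, if any, is under 1% on the SDs assumed above.
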